8.1.2 Minimal Residual Disease (CLL subjects in phase 2 – cohort B)

If the subject's physical examination findings, laboratory evaluations, and radiographic evaluations suggest that PR, CR or CRI has been achieved, a peripheral blood by flow cytometry sample to evaluate MRD should be done between 8-12 weeks from the time of supportive clinical assessments including CT imaging of suspected PR, CR or CRI.

A peripheral blood sample testing for minimal residual disease (MRD) will be done at screening and end of treatment visit or if not taken at the EoT visit, then it can be drawn at SFU visit.

Samples for the MRD tests will be sent to the central laboratory for analysis as per instructions in the laboratory manual.

8.1.3 Clinical laboratory assessments

See [Table 10](#) for the list of clinical safety laboratory tests to be performed and to the SoA for the timing and frequency. All protocol-required laboratory assessments, as defined in the table, must be conducted in accordance with the laboratory manual and the SoA.

The Investigator should make an assessment of the available results with regard to clinically relevant abnormalities. The laboratory results should be signed and dated and retained at centre as source data for laboratory variables.

For information on how AEs based on laboratory tests should be recorded and reported, see Section [8.3.7](#).

Additional laboratory samples may be collected if clinically indicated at the discretion of the Investigator. The date, time of collection and results (values, units and reference ranges) will be recorded on the appropriate eCRF.

The clinical chemistry, hematology (see paragraphs below for specific requirements for CLL subjects in phase 2 – cohort B), pregnancy test, coagulation, urinalysis, hepatitis, HIV and serum immunoglobulin levels analyses will be performed locally at the visits as indicated in the SoA (see [Table 1](#), [Table 2](#) and [Table 3](#)), therefore sample volumes may vary according to local practice. If screening assessment clinical chemistry, hematology, coagulation and urinalysis are performed within 5 days prior to the baseline visit (i.e. first dose day: Phase 1 portion- at Cycle 0 Day 1; Phase 2 portion- at Cycle 1 Day 1), they do not need to be repeated at the baseline visit. T/B/NK cell count (i.e., CD3, CD4, CD8, CD19, CD16/56) will be performed at the central laboratory, samples will be collected, labelled, stored, and shipped as detailed in the Laboratory Manual.

All samples will be used up, or disposed of after analyses.

Additional laboratory tests requirement for CLL subjects in phase 2 – cohort B only:

Hematology will be evaluated at the central laboratory and will include a complete blood count (CBC) with differential including, but not limited to white blood cell count, hemoglobin, hematocrit, platelet count, ANC, and ALC. Any missing central laboratory blood samples should be redrawn as soon as possible. In the event that the missing central laboratory sample is unrecoverable, local laboratory results will be collected, if available, and entered in the clinical database. β 2-microglobulin: peripheral blood samples will be collected and sent to the central laboratory for β 2-microglobulin test.

Cytogenetics and FISH Panel: screening peripheral blood (required) will be sent to a central laboratory to be tested for Del 17p, Del 13q, trisomy 12, Del 11q by FISH and stimulated karyotyping. A blood sample for FISH evaluation will also be drawn when a subject has disease progression at the EoT or SFU visits.

Genetic and molecular prognostic molecules: screening peripheral sample will be sent to central laboratory for sequencing of immunoglobulin heavy-chain variable (IGHV) and p53 mutational status. If the progression peripheral blood sample is not taken at the EoT visit, then it can be drawn at the SFU visit. Any systematic anti-cancer treatment(s) between confirmed progression and SFU visit with sample drawn should be documented.

Table 10 Laboratory variables

Clinical Chemistry ^a	
Calcium	Urea or blood urea nitrogen
Chloride	Uric acid
Magnesium	Creatinine
Phosphate/Phosphorus	Total bilirubin
Potassium	Glucose
Sodium	Albumin
AST	Total protein
ALT	Triglycerides
Alkaline phosphatase (ALP)	Cholesterol
Gamma glutamyl transferase (GGT)	Lactate dehydrogenase (LDH)
Haematology ^b	
White blood cell (WBC) count with differential	Platelet count
Red blood cell (RBC) count	Absolute neutrophil count (ANC)
Haematocrit	Absolute lymphocyte count (ALC)

Haemoglobin	
Urinalysis	
pH	Bilirubin
Specific gravity	Protein
Glucose	Ketones
Blood	
Pregnancy Test (females of childbearing potential only)	
Urine human chorionic gonadotropin (hCG) or Serum β hCG	
Hepatitis B and C Testing ^c	
HBsAg	Hepatitis B surface antibody (HBsAb)
Anti-HBc	Hepatitis C (hepatitis C virus [HCV]) antibody
Hepatitis B PCR (clinically indicated)	Hepatitis C PCR (clinically indicated)
Coagulation	
Coagulation tests: prothrombin time (PT)	Activated partial thromboplastin time (aPTT)
Fibrinogen	
Other Tests	
T/B/NK Cell Count	Serum immunoglobulin levels
HIV antibody	β 2-microglobulin ^d
Cytogenetics and FISH Panel ^{d,e}	Genetic and molecular prognostic molecules ^{d,f}

a. In case a subject shows an AST or ALT \geq 3xULN together with total bilirubin \geq 2xULN please refer to [Appendix D](#). ‘Actions required in cases of increases in liver biochemistry and evaluation of Hy’s Law’, for further instructions.

b. Hematology will be evaluated at the central laboratory for CLL subjects in phase 2 – cohort B.

c. Hepatitis serology testing must include HBsAg, HBsAb, anti-HBc and hepatitis C (HCV) antibody. In addition, any subjects testing positive for anti-HBc must have quantitative PCR testing for HBV DNA during screening and monthly basis from Cycle 2 through 19. After Cycle 19, monitoring will occur every 3 months. HBV monitor should continue until 12 months after last dose of study drug (see [Table 1](#), [Table 2](#), [Table 3](#) and exclusion criterion #7). Any subject with a rising viral load (above lower limit of detection) should discontinue study drug and have antiviral therapy instituted and a consultation with a physician with expertise in managing hepatitis B. Since IVIG may cause false positive hepatitis serology, monthly PCR testing is not required in subjects who are currently receiving or received prophylactic IVIG within 3 months before study enrollment and have a documented negative anti-HBc test before the initiation of IVIG therapy. PCR testing should be performed when clinically indicated (e.g., in the setting of rising transaminase levels). Refer to [Table 1](#), [Table 2](#) and [Table 3](#) regarding monitoring of subjects who are anti-HBc positive or who have a known history of HBV.

Subjects with a known history of hepatitis C or who are hepatitis C antibody positive should have quantitative PCR testing for HCV RNA performed during screening. No further testing is necessary if the PCR results are negative at screening.

- d. These tests will be performed at the central laboratory and for CLL subjects in cohort B only.
- e. Cytogenetics and FISH Panel include Del 17p, Del 13q, trisomy 12, Del 11q by FISH and stimulated karyotyping.
- f. Genetic and molecular prognostic molecules panel include, but is not limited to, sequencing of p53 mutations, immunoglobulin heavy-chain variable (IGHV) mutational status.

8.1.4 B-Symptoms

B-symptoms are constitutional symptoms defined as any one or more of the following disease-related symptoms or signs:

- Unintentional weight loss of 10% or more within the previous 6 months
- Significant fatigue (i.e., ECOG performance status 2 or worse; inability to work or perform usual activities)
- Fevers >100.5°F or 38.0°C for \geq 2 weeks without other evidence of infection
- Night sweats for >1 month without evidence of infection

B-symptoms is part of tumor response assessment for CLL subjects per [Hallek 2018](#).

B-symptoms should not be reported as AEs. Worsening is generally considered a symptom (but not an objective criterion) of progression.

8.2 Safety assessments

Standard collection of AE data and other study variables (eg. vital signs, 12 lead ECG, blood sampling for haematology, clinical chemistry and coagulation, urinalysis etc.) will be carried out according to the Schedule of Activities.

8.2.1 Clinical safety laboratory assessments

Clinical safety laboratory assessment is included in [Table 10](#) and specified into the SoA for the timing and frequency.

8.2.2 Physical examinations

The physical examination includes height (Screening only) and weight, and examination of the skin, eyes, ears, nose, throat, lungs, heart, abdomen, extremities, musculoskeletal, nervous, lymphatic system, and general appearance. The nervous system examination will include attention to neurologic signs and symptoms of PML. The lymphatic system examination will include bidimensional measurements of palpable lymph nodes. Enlargement of the spleen and liver will be assessed by measuring the costal margin and past-medioclavicular line, respectively. Only a qualified healthcare provider should perform the lymphatic system examination. As much as possible, the same person should perform all the lymphatic exams for a given subject.

Changes from baseline abnormalities should be recorded in subject notes. New or worsened clinically significant abnormalities should be recorded as AEs on the Adverse Event eCRF.

Physical examination will be performed at timelines as specified in the SoA. Investigators should pay special attention to clinical signs related to previous serious illnesses, new or worsening abnormalities may qualify as adverse events, see Section [8.3.7](#) for details.

8.2.3 Vital signs

Vital signs (Blood pressure, pulse rate, and body temperature) should be assessed after at least 5 minutes of rest for the subject in a quiet setting without distractions (e.g., television, cell phones).

Changes from baseline abnormalities should be recorded in subject notes. New or worsened clinically significant abnormalities should be recorded as AEs on the Adverse Event eCRF.

8.2.4 Electrocardiograms

Twelve-lead ECG will be obtained as outlined in the SoA (see Section [1.1](#)) using an ECG machine that automatically calculates the heart rate and measures PR, QRS, QT, and QTc intervals. Study -related ECG should be done after the subject has been resting supine for at least 10 minutes. A standardized ECG machine should be used and the subject should be examined using the same machine throughout the study if possible.

On the intensive PK sampling days (Cycle 0 Day 1 and Cycle 1 Day 8), the assessment will be performed at 1-2 hours post (morning) dose. The timing and number of ECGs may be altered depending on the emerging PK and safety profile.

After paper ECGs have been recorded, the investigator or designated physician will review each of the ECGs and may refer to a local cardiologist if appropriate. A paper copy should be filed in the patient's medical records.

If an abnormal ECG finding at screening or baseline is considered to be clinically significant by the investigator, it should be reported as a concurrent condition. For all ECGs details of rhythm, ECG intervals and an overall evaluation will be recorded.

8.2.5 ECOG performance status

ECOG performance status will be assessed at screening, prior to the first dose of study treatment and at all visits thereafter according to ECOG criteria as follows: It is recommended, where possible, that a subject's performance status be assessed by the same person throughout the study.

Grade ECOG

- 0 Fully active, able to carry on all pre-disease performance without restriction
- 1 Restricted in physically strenuous activity but ambulatory and able to carry out work of a light or sedentary nature, e.g., light house work, office work
- 2 Ambulatory and capable of all self-care but unable to carry out any work activities. Up and about more than 50% of waking hours
- 3 Capable of only limited self-care, confined to bed or chair more than 50% of waking hours
- 4 Completely disabled. Cannot carry on any self-care. Totally confined to bed or chair
- 5 Dead

8.3 Collection of adverse events

The Principal Investigator is responsible for ensuring that all staff involved in the study are familiar with the content of this section.

The definitions of an AE or SAE can be found in [Appendix B](#).

AE will be reported by the subject (or, when appropriate, by a caregiver, surrogate, or the subject's legally authorized representative).

The investigator and any designees are responsible for detecting, documenting, and recording events that meet the definition of an AE or SAE. For information on how to follow/up AEs see Section [8.3.3](#).

8.3.1 Method of detecting AEs and SAEs

Care will be taken not to introduce bias when detecting AEs and/or SAEs. Open-ended and non-leading verbal questioning of the subject is the preferred method to inquire about AE occurrences.

8.3.2 Time period and frequency for collecting AE and SAE information

AEs and SAEs will be collected from time of signature of informed consent form until 30 days after the last dose of study treatment or the start of new anticancer therapy (whichever comes first). After this period, investigators should report SAEs or other AEs of concern that are believed to be related to prior treatment with study treatment.

All SAEs that occur during the reporting period should be followed to resolution or until the investigator assesses the subject as stable, or until the subject is lost to follow up or withdraws

consent. Resolution/stable means the subject has returned to baseline state of health or the investigator does not expect any further improvement or worsening of the event.

All SAEs/AESIs will be recorded and reported to the sponsor or designee within 24 hours. The investigator will submit any updated SAE/AESI data to the sponsor within 24 hours of it being available.

Investigators are not obligated to actively seek AE or SAE in former study subjects. However, if the investigator learns of any SAE, including a death, at any time after a subject's last visit and he/she considers the event to be reasonably related to the study treatment or study participation, the investigator may notify the sponsor.

The method of recording, evaluating, and assessing causality of AE and SAE and the procedures for completing and transmitting SAE reports are provided in [Appendix B](#).

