8.3.12 Handling of deaths

All deaths that occur during the study, or within the protocol-defined follow-up period after the administration of the last dose of investigational product, should be reported as follows:

- Death, which is unequivocally due to disease progression, should be communicated to the study monitor at the next monitoring visit and should be documented in the eCRF module, but should not be reported as a SAE during the study
- Where death is not due (or not clearly due) to disease progression of the disease under study, the AE causing the death should be reported to the study monitor as an SAE within 24 hours. The report should contain a comment regarding the co-involvement of progression of disease, if appropriate, and should assign a single primary cause of death together with any contributory causes
- Deaths with an unknown cause should always be reported as a SAE but every effort should be made to establish a cause of death. A post-mortem may be helpful in the assessment of the cause of death, and if performed a copy of the post-mortem results (with translation of important parts into English) should be reported in an expedited fashion to an AstraZeneca representative within the usual timeframes.

Deaths occurring after the protocol-defined reporting period (30 days after the last dose of study treatment) should be documented in the Death page. If the death occurred as a result of an event that started after the defined follow-up period and the event is considered to be due to a late-onset toxicity to study treatment, then it should also be reported as an SAE.

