8.4 Safety reporting and medical management

8.4.1 Reporting of serious adverse events

All SAEs have to be reported, whether or not considered causally related to the investigational product, or to the study procedure(s). All SAEs will be recorded in the CRF.

If any SAE occurs in the course of the study, then Investigators or other site personnel inform the appropriate AstraZeneca representatives within one day i.e., immediately but **no later than 24 hours** of when he or she becomes aware of it.

The designated AstraZeneca representative works with the Investigator to ensure that all the necessary information is provided to the AstraZeneca Patient Safety data entry site **within 1**

calendar day of initial receipt for fatal and life-threatening events **and within 5 calendar days** of initial receipt for all other SAEs.

For fatal or life-threatening adverse events where important or relevant information is missing, active follow-up is undertaken immediately. Investigators or other site personnel inform AstraZeneca representatives of any follow-up information on a previously reported SAE within one calendar day i.e., immediately but **no later than 24 hours** of when he or she becomes aware of it.

Once the Investigators or other site personnel indicate an AE is serious in the EDC system, an automated email alert is sent to the designated AstraZeneca representative.

If the EDC system is not available, then the Investigator or other study site staff reports a SAE to the appropriate AstraZeneca representative by telephone.

The AstraZeneca representative will advise the Investigator/study site staff how to proceed.

For further guidance on the definition of a SAE, see [Appendix B](#) of the Clinical Study Protocol.

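### Protocol Section 8.3.2 both calls for and makes optional the reporting of treatment-related SAEs learned of after a subject's last visit

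*Protocol*

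**What the plan says.** Protocol Section 8.3.2 collects AEs and SAEs from consent to 30 days after the last dose or to the start of new anticancer therapy, whichever is earlier. The same paragraph continues: "After this period, investigators should report SAEs or other AEs of concern that are believed to be related to prior treatment with study treatment". No end date is given.

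The third paragraph puts SAEs and AESIs on a 24-hour reporting timeline.

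The fourth paragraph turns to people who have left the study: "Investigators are not obligated to actively seek AE or SAE in former study subjects". It then deals with events that reach the investigator anyway. The trigger is "if the investigator learns of any SAE, including a death, at any time after a" subject's last visit, and where "he/she considers the event to be reasonably related to the study treatment or study participation, the investigator may notify the sponsor".

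Two other sections bear on this:

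- Section 8.3.12 covers deaths after the reporting period. Where the causal event began after that period and is "considered to be due to a late-onset toxicity to study treatment, then it should also be reported as an SAE".
- Section 8.4.1 states a general duty: "All SAEs have to be reported, whether or not considered causally related to the investigational product". Its 24-hour instruction is written for SAEs that occur during the study.

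**The concern.** The fourth paragraph is not only the counterpart of having no duty to search for events. It concerns an SAE that the investigator already knows of and has already judged related to treatment. The first paragraph says such an event should be reported. A site that reads the fourth paragraph can hold back the same event and still be following the protocol.

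After the last visit the sponsor has no scheduled contact through which to find these events, so what it learns depends on the sites. Protocol Section 2.3.2.2 lists second primary malignancies as an important identified risk and mentions HBV reactivation under infections; either could come to light late. Appendix A 1 calls prompt SAE notification by investigators essential to legal and ethical duties, which fits poorly with an optional report of a known, related SAE.

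**Working it through.** No arithmetic underlies the point. The check is whether the two rules overlap, for whom, and whether another section settles the matter.

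| Rule | Starts | Ends | Events | Strength |
|---|---|---|---|---|
| 8.3.2, paragraph 1 | End of collection window | Not stated | Related SAEs, other related AEs of concern | *should report* |
| 8.3.2, paragraph 4 | Subject's last visit | Not stated | Related SAEs, including deaths | *may notify* |
| 8.3.12 | End of reporting period | Not stated | Deaths from late-onset toxicity | *should* be reported |
| 8.4.1 | Not stated; timeline tied to the study | Not stated | All SAEs | *have to* be reported |

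**Step 1, overlap.** Paragraph 1 runs from the end of the window without limit. Paragraph 4 runs from the last visit without limit. Where the last visit is later than the end of the window, only paragraph 1 applies in between. From the last visit on, a related SAE satisfies both rules.

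**Step 2, who reaches the overlap early.** Under Section 7.1.2 and the footnotes to Tables 1 to 3, Cohort A, Cohort B and Phase 1 MCL subjects are followed for progression and then contacted about every 12 weeks for survival. They stay under *should report* alone until their last visit. In Phase 1, the Table 1 footnotes limit disease and survival follow-up to MCL. For the other Phase 1 subjects the safety visit at 30 (+7) days is the last regular visit. If the window closes at day 30, the interval under *should report* alone is at most 37 − 30 = 7 days.

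**Step 3, size of that group.** Planned enrolment is about 12 in Phase 1 and 33 + 60 = 93 in Phase 2. Phase 1 subjects without MCL are therefore at most about 12 of 12 + 93 = 105, or 11%. The documents do not give the actual split by disease.

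**Step 4, does another section settle it?** Section 8.3.12 says *should*, but only for deaths. Section 8.4.1 is broad, yet its timeline is for SAEs during the study, so it does not clearly reach events after the last visit. Protocol Section 4.4 deals with subjects who stay on treatment after the final data cut-off and repeats the 30-day or new-therapy limit, without a rule for later events. None of these removes the conflict.

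**Step 5, which outputs depend on it.** SAP Section 3.2.2.1 closes the TEAE window at the same point as the collection window. SAP Section 4.2.3.3 sends AEs more than 30 days after discontinuation to the listings. Late related SAEs can therefore change the listings but not the TEAE tables, and ORR does not use them.

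**The case against.** The strongest reply is that the two sentences have different triggers, so little is left in conflict. Paragraph 1 starts at the end of the window, paragraph 4 at the last visit, and most subjects have long follow-up between the two. Late-toxicity deaths have their own *should* in Section 8.3.12. Appendix B 2 counts follow-up as a study phase in the SAE definition, Section 8.3.11 treats new cancers as AEs, and Section 8.4.1 says that all SAEs have to be reported. No planned table rests on these events.

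Much of this stands, and it sets the scope. A reader might infer that every related SAE after the collection window is optional to report. The text does not support that: until the last visit only *should report* applies.

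A reader might also set the 30-day window against the 12 months of post-treatment HBV monitoring and conclude that about 11 of those 12 months are exposed. That does not follow. Subjects still having PCR tests scheduled by the protocol are not plainly former subjects, and the protocol does not say whether such a test counts as a visit. The monitoring covers only anti-HBc positive, HBsAg negative subjects. The window can also close before day 30 if new therapy starts, so 11 months is not even an upper limit.

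The reply does not remove the overlap after the last visit. There, one section gives two answers for an event already known and already judged related.

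**Conclusion.** The point holds as an internal inconsistency of limited scope. It concerns treatment-related SAEs that the investigator learns of after a subject's last visit, mainly non-fatal ones. For deaths from late-onset toxicity, Section 8.3.12 already says *should*, and *may* in Section 8.3.2 conflicts with it. The gap is widest for Phase 1 subjects without MCL.

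The effect is on safety reporting and on how complete the AE listings are. A reader might infer that the efficacy result or the TEAE rates are at risk; they are not. The number of events that could go unreported cannot be derived from the documents.

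Two assumptions matter. First, the 12-weekly survival contacts, which may be by telephone, are taken to count as visits; if they do not, the overlap starts earlier for subjects who have progressed. Second, *should* is read as an expectation to report, stronger than *may* but not worded as an absolute requirement.

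**What to change.** Reconcile the fourth paragraph of Section 8.3.2 with its first paragraph and with Section 8.3.12, so that one duty, *should report*, applies to any related SAE learned of after a subject's last visit. The sentence that investigators need not search for events in former subjects can stay. State whether the 24-hour timeline in Section 8.3.2 applies to these reports.

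This is a wording change for the next protocol amendment, which needs IRB/IEC approval, together with a notice to sites. It adds no visits, procedures or scheduled data collection and leaves the planned analyses unchanged.
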